To vaccinate healthy elderly with two distinct pneumococcal vaccines, collect longitudinal blood samples and assess pneumococcal-specific antibody responses.

Hypothesis: We hypothesize that PPSV23 and PCV13 differentially activate the circulating immune cells and the blood transcriptome of healthy elderly individuals.

Rationale: Our studies in healthy young adults showed that Fluzone® and pneumococcal vaccines activate different immune cell subsets *in vivo* (data not shown). In addition, we showed that individuals vaccinated with PPSV23 and Fluzone® display a different blood transcriptome at

day 1 (Fig. 1). Thus, different vaccines might induce the generation of specific antibodies through different mechanisms. Here, our goal is to generate profiles of responses to conjugated and unconjugated polysaccharide-based pneumococcal vaccines and to correlate the elicited immune profiles with antibody responses.

Approach: The overall flow of the work is illustrated in Fig. 1. We will examine whether the induction of pneumococcus

Figure 1. Overview of work.

serotype-specific antibodies at day 28 correlates with the activation of T cells (as measured by flow cytometry) at day 10 and the activation of APCs at day 1 (measured by flow cytometry and transcriptomics). In a cohort of 40 healthy elderly naïve to pneumococcal vaccination we will: 1) vaccinate with either PPSV23 or PCV13; 2) longitudinally collect blood, serum and blood cell samples from each group; 3) perform the experiments that require immediate processing, such as flow cytometry analysis; and 4) cryopreserve all the other samples for downstream genomics and cellular immunology studies. Our earlier studies permitted us to draw robust conclusions on the transcriptome profiles in blood cells and on the role of Tfh activation in the generation of Fluzone®-specific antibody responses.

Elderly Populations: We will focus on the healthy adults >60 years of age that meet eligibility criteria (Section 4). 40 healthy community-dwelling elderly from areas surrounding the University of Connecticut Health Center will be accrued. Volunteers will be randomized to receive either the PCV13 or PPSV23 vaccine. CDC currently recommends that healthy older adults with no history of previous pneumococcal vaccination receive PCV13 followed by PPSV23 at least 12 months later. All participants will be offered a boost dose with the other vaccine at one to two years later, at no cost to them.

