To investigate our hypothesis we will apply RNA-seq, rather than DNA microarrays, to generate transcriptional profiles, as this will enable quantitative assessment of both coding RNAs and ncRNAs. We will also use ATAC-seq to resolve the epigenetic landscape of immune cells in healthy elderly in the context of vaccine responses.

Approach:

1. *Blood transcriptomics by RNA-seq:* We will carry out RNA-seq of whole blood samples at baseline, day 1 and day 10. Samples collected from days 28 and 60 will be kept frozen for future studies. RNA-seq on purified cell subsets will be performed using purified cells from the five lowest and five highest responders for each vaccine. Sequencing will be performed at JAX-GM with an Illumina HiSeq2500.
2. *Blood epigenomics analysis by ATAC-seq:* We will analyze PBMCs, CD4+ T cells, monocytes, CD1cDCs and B cells (25×10^3 cells per assay). We are also developing assays with lower cell numbers to address the scarcity of some populations, and are encouraged by reports of single cell ATAC-seq [17]. We will generate a database describing the DNA accessibility landscape of major immune-cell subsets from elderly individuals at steady state. The data will also include the DNA accessibility landscape of monocytes, T and B cells analyzed at different time points following vaccination with the two pneumococcal vaccines. For these in-depth studies, we will select the five highest and five lowest responders for each vaccine.

Correlative analysis: We will correlate the increased levels of day 28 anti-pneumococcal antibodies as defined in Aim 1 with all the parameters collected in this aim. Parameters include: 1) cellular composition at baseline, day 1 and day 10 post-vaccination; 2) transcriptome analysis on blood and purified immune cell subsets at baseline, day 1 and day 10; 3) ATAC-seq data on PBMCs and purified cell subsets at the different time points and 4) pneumococcal colonization at baseline and at day 28. A detailed description of the statistical approaches is given below (see Integrative Data Analysis section).

1.3 Specific Aim 3

To examine the functional status of immune cells in the elderly stratified according to their pneumococcal vaccine responder status.

Hypothesis: We hypothesize that lack of *in vivo* response to PPSV23 and PCV13 depends on alterations to APCs, Tfh cells or B cells.

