3 STUDY DESIGN

This prospective, single-site, randomized, then open-label study is designed to develop a detailed transcriptional and epigenetic profile of the immune response to pneumococcal vaccination with conjugated and non-conjugated polysaccharide vaccines in the senescent immune system of older adults. This knowledge may lead to development of more effective vaccines through increased understanding of the effects of immunosenescence on mechanisms of immune response to pneumococcal vaccination in the elderly.

Forty (40) healthy adults ages 60 and older that have never received pneumococcal vaccination, will be randomized in a 1:1 ratio to receive Prevnar-13 (Pfizer), a conjugated 13-valent vaccine or Pneumovax 23 (Merck), a non-conjugated 23-valent vaccine. Following randomized assignment of vaccine, the study will be open-label.

The first six (6) study visits are planned to occur over 67 days at Days -7, 0, 1, 10, 28 (± 3 d) and 60 (± 5 d). Participants will provide blood samples for transcriptional, epigenetic and biological analyses pre- and post-vaccination.

One to two years after receiving the randomly-assigned vaccination, participants may opt to receive administration of a second pneumococcal vaccine with the vaccine that they did not receive by random assignment at Visit 2 (Day 0). This second vaccine will be provided at no charge to the participant. Administration of this vaccine will occur at an optional Visit 7 for participants who choose to receive the second vaccine and will be scheduled at the participant's convenience one-two years after receiving the first pneumococcal vaccine.

If the participant opts to receive the second vaccine within the study and attends optional Visit 7, blood samples for genomic and biologic analysis will be collected at the visit.

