8 INTEGRATIVE DATA ANALYSIS

8.1 Statistical Methods

The breadth and magnitude of IgG titers will be analyzed individually and together using best-response and multivariate U-statistic approaches [4, 97]. Differences among groups (e.g., responder status) and/or time of immunological variables (e.g., flow, RNAseq) will be assessed using generalized linear mixed-model analyses with appropriate distributional assumptions (e.g., normal, negative binomial) and link functions (e.g., identity, log). Propensity scores [98] will be adjusted for possible confounds such as gender, age, race and ethnicity, while the Bonferroni correction or Benjamini and Hochberg false discovery rate (FDR) will account for multiple testing [99]. Correlation of clinical and immunological variables will be conducted using the Pearson or Spearman Correlation Coefficient depending on whether or not the assumptions of linearity and homoscedasticity are met. For class prediction, a variety of methods including k-nearest neighbors, radial basis machine, random forests, boosted trees and support vector machines will be employed and validated using leave-one-out cross-validation. Unsupervised analysis of high dimensional data will be conducted using heatmaps, hierarchical cluster analysis and principal component analysis. Lastly, attrition and missing data are issues in longitudinal [100] and elderly studies [101]. "Missingness" will be characterized and multiple imputation applied when appropriate [102-104]. Drs. [name] (JAX) and [name] (SIDRA) will assist with statistics and bioinformatics as needed.

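### Section 8.1 does not say whether antibody–feature correlations are computed within vaccine or across both; post-vaccination features need a vaccine-adjusted correlation

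*Combined protocol and SAP*

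**What the plan says.** Section 8.1 names a two-variable coefficient and bases the choice between the two types only on linearity and homoscedasticity: "Correlation of clinical and immunological variables will be conducted using the Pearson or Spearman Correlation Coefficient". It names no partial, stratified or model-based form for the correlations.

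The correlations are set up in Section 1:
- Section 1.1 asks whether the induction of "serotype-specific antibodies at day 28 correlates with the activation of T cells (as measured by flow cytometry) at day 10", and also with APC activation at Day 1.
- Section 1.2, under Correlative analysis, states: "We will correlate the increased levels of day 28 anti-pneumococcal antibodies as defined in Aim 1 with all the parameters collected in this aim". For methods it refers the reader to the Integrative Data Analysis section, which is Section 8.

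Participants "will be randomized in a 1:1 ratio to receive Prevnar-13 (Pfizer), a conjugated 13-valent vaccine or Pneumovax 23 (Merck"), so the 40 divide into 20 and 20. The confounders named in Section 8.1 are gender, age, race and ethnicity, in a sentence about propensity scores. Section 1.1 adds CMV status to the analysis. Responder status is the only example of a group factor for the mixed models. Vaccine is not named in any of these places.

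**The concern.** On the plan's own account, vaccine may move both sides of the correlation. For the immune features, Section 1.1 says: "We hypothesize that PPSV23 and PCV13 differentially activate the circulating immune cells". For antibody, Section 2.1 describes PCV13 as the more immunogenic vaccine for some serotypes. In addition, the response score in Section 1.1 counts serotypes, while Section 5.1 notes 11 serotypes that only PPSV23 contains.

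If vaccine shifts both a post-vaccination feature and the antibody measure, a coefficient over all 40 people combines two things: the difference between vaccines, and the association among people given the same vaccine. Only the second answers the Aim 1 question. Shifts in the same direction can produce a correlation where none exists within either arm; shifts in opposite directions can hide one that does. Because Section 8.1 leaves the choice open, it could be made after the data are seen, and the two analyses can disagree.

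**Working it through.** **Plan's own figure.** There is none to reproduce. The only power statement (Section 8.2) concerns two-sample comparisons of gene expression; none is given for the correlations.

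**Inputs.** 20 per arm (Section 3). The following are assumptions, because the documents give no values: two-sided 0.05 before any multiplicity correction, no dropout, normal variables with within-arm SD 1, and vaccine shifts dx (feature) and dy (antibody) in within-arm SD.

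**Step 1: expected coefficient across both arms.** With equal arms, vaccine adds dx·dy/4 to the covariance, and dx²/4 and dy²/4 to the variances. With within-arm correlation r:

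r across arms = (r + dx·dy/4) / √[(1 + dx²/4)(1 + dy²/4)]

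- r = 0, shifts 0.5 and 0.5: 0.0625/1.0625 = 0.06
- r = 0, shifts 1 and 1: 0.25/1.25 = 0.20
- r = 0, shifts 1.5 and 1.5: 0.5625/1.5625 = 0.36
- r = 0.5, shifts +1 and −1: (0.5 − 0.25)/1.25 = 0.20
- r = 0.5, shifts +1.5 and −1.5: (0.5 − 0.5625)/1.5625 = −0.04
- r = 0.5, shifts +2 and −2: (0.5 − 1)/2 = −0.25
- r = 0.5, feature shift 1 only: 0.5/√1.25 = 0.45
- r = 0.5, shift 1.5 in one variable only: 0.5/√1.5625 = 0.40

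**Step 2: how often p < 0.05.** Simulation, 40,000 trials of 20 + 20 per row. The adjusted column is the partial correlation after centring each arm.

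| True within-arm r | Shifts, feature / antibody (SD) | Pooled Pearson | Pooled Spearman | Vaccine-adjusted |
|---|---|---|---|---|
| 0 | 0 / 0 | 4.9% | 5.1% | 4.8% |
| 0 | 0.5 / 0.5 | 6.5% | 6.5% | 4.9% |
| 0 | 1 / 1 | 24.2% | 24.6% | 5.0% |
| 0 | 1.5 / 1.5 | 67.8% | 70.5% | 4.9% |
| 0.5 | 0 / 0 | 92.4% | 88.9% | 91.7% |
| 0.5 | +1 / −1 | 20.2% | 16.1% | 91.6% |
| 0.5 | +1.5 / −1.5 | 3.7% | 8.0% | 91.5% |
| 0.5 | +2 / −2 | 36.1% (wrong sign) | 54.7% | 91.9% |
| 0.5 | 1 / 0 | 84.2% | 78.6% | 91.6% |
| 0.5 | 0 / 1.5 | 73.6% | 66.1% | 91.4% |

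Spearman gives no protection. Nor does the planned FDR or Bonferroni correction remove the problem, because the pooled association is real; it reflects the vaccine given.

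**Step 3: cost of adjusting.** Smallest r detectable with 80% power, by Fisher z: tanh[(1.960 + 0.842)/√(n − 3)], with one further degree of freedom removed for the vaccine term.

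- Unadjusted, n = 40: tanh(2.802/√37) = 0.43
- Vaccine-adjusted, n = 40: tanh(2.802/√36) = 0.44
- Within one arm, n = 20: tanh(2.802/√17) = 0.59

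**The case against.** The strongest reply is that the plan never says it will pool. A reader might infer a pooled analysis from "In a cohort of 40 healthy elderly naïve to pneumococcal vaccination we will" in Section 1.1, but that sentence introduces the operational steps (vaccinating, sampling, processing, freezing). The correlation question before it carries no sample size. Other text works by vaccine: Section 1.2 picks the five highest and five lowest responders for each vaccine, Section 1.3 separates responders and non-responders by vaccine and uses cohort for the PCV13 arm alone, and Section 8.2 counts twenty per cohort. A within-vaccine correlation is a natural reading. This stands: the defect is an unspecified analysis. Selecting samples by vaccine still does not specify how a correlation is computed.

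Second, a different pathway to antibody need not mean a different antibody level. If the response score is ranked within vaccine, the antibody shift disappears and pooling can only attenuate, as in the rows with a shift in one variable. The same holds for baseline features, which the randomised vaccine cannot affect. This also stands, and it limits the point to post-vaccination features with an antibody measure not ranked within vaccine. The documents do not say which ranking applies.

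Third, the effect is small for small shifts: at 0.5 SD, rejection is 6.5%. That is correct.

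Fourth, the n = 40 figures suit flow cytometry and whole-blood features. Purified-cell RNA-seq and the in-depth ATAC-seq use about 20 selected people (10 per vaccine), so the figures do not carry over to them.

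**Conclusion.** The point holds as a gap in specification with a better method available at almost no cost. Section 8.1 names only a two-variable coefficient and does not say whether it is taken within vaccine or across both. Across both arms, for post-vaccination features, false positives would be about 24% at equal 1 SD shifts and 68% at 1.5 SD. With a true within-arm r of 0.5 and opposite 1 SD shifts, power would fall from about 92% to 20%. These figures rest on assumed shifts; the documents expect differences between the vaccines but give no sizes.

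Two stronger readings are not supported. A reader might infer that the plan commits to a pooled coefficient; it is silent. A reader might also infer that the reported correlation is likely to have the wrong sign. At opposing shifts of 1.5 SD the expected value is −0.04, in effect zero. A reversal of note (−0.25, significant with the wrong sign in 36% of trials) needs opposing shifts of about 2 SD, and nothing in the documents supports shifts that large.

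**What to change.** In Section 8.1:

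1. Make the main antibody–feature association vaccine-adjusted: a partial Pearson or Spearman correlation, or a linear model of Day 28 response on feature and vaccine. Add a vaccine-by-feature term to check whether the slopes differ, since Section 1 expects the two vaccines to activate different pathways.
2. Report arm-specific estimates as supportive.
3. Label any unadjusted coefficient across both arms as descriptive.
4. State whether the antibody score is ranked within vaccine or across vaccines, and on which serotypes.

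The cost is wording and about one degree of freedom for the adjusted estimate (smallest detectable r 0.44 against 0.43); the interaction check uses one more. Arm-specific estimates are less precise (about 0.59 with 20 per arm), which is why they should support the adjusted estimate and not replace it. No additional participants, samples or assays are needed.

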1 OBJECTIVES

The goal of our project is to assess the alterations to immune blood cells associated with the response of healthy elderly subjects to two pneumococcal vaccines, unconjugated (PPSV23) and conjugated (PCV13) polysaccharide vaccines. APCs, Tfh and B-cell subsets will be analyzed at different time points after vaccination. Phenotype, function, transcriptome and epigenetic analyses will be carried out on selected high responders and non-responders. These studies would provide us with the unique opportunity to investigate the human immune response of elderly individuals—a primary target for these vaccines—to a TI and TD antigen. Furthermore, a detailed

assessment of circulating immune cells from healthy elderly could enable us to identify the immune deficits that underpin non-responsiveness; such insights could help to improve vaccine efficacy.

Our detailed analyses will include: i) RNAseq of whole blood and cell subsets, to generate profiles of both coding RNAs and ncRNAs [1]; ii) ATACseq, to assess chromatin state and determine whether the genome is poised towards specific immune responses; and iii) *in vitro* cellular immunology studies to determine the function of APCs, T cells and B cells in vaccine-induced immune responses. We will keep all samples to further assess genotype using high-density SNP chips. Note that this study is not designed to establish baseline phenotypes predictive of vaccine responsiveness.

We expect to find that PPSV23 and PCV13 will activate different pathways leading to pneumococcal-specific antibody responses. Our hypothesis is that the PCV13 response pattern will resemble the response pattern we observed with Fluzone® inasmuch as both vaccines are considered to be TD. Significant differences in responsiveness can, however, be brought by molecular components specific to each vaccine, i.e., the polysaccharide component of PCV13 or the viral nucleic acids that might be included in Fluzone®. Our preliminary data *in vivo* in young adult volunteers and *in vitro* with APC subsets suggest that PPSV23 might trigger different immune pathways to elicit specific antibody responses. While the consensus is that its effects are TI, our observed induction of activated T cells *in vivo* and the presence of mutated IgG and IgA hints to more complex mechanisms, which might include both TD and TI mechanisms of B-cell activation [2].

[figure not shown]
1.1 Specific Aim 1

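### Leave-one-out validation pushes classifier accuracy below its true value when the classes are equal-sized, as in the five highest v five lowest responder groups

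*Combined protocol and SAP*

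**What the plan says.** Section 8.1 (Statistical Methods) names five families of classifier in an open-ended list and says they "will be employed and validated using leave-one-out cross-validation". It does not give the data layer, time point or classes to be predicted. Nor does it say whether gene selection and tuning are repeated in each fold, which accuracy measure is reported, or how chance is to be excluded.

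Section 1.2 (Specific Aim 2) fixes the size of some of the candidate data sets. For sorted cells, "RNA-seq on purified cell subsets will be performed using purified cells from the five lowest and five highest responders for each vaccine". For the ATAC-seq work, "For these in-depth studies, we will select the five highest and five lowest responders for each vaccine". Whole blood is treated differently: "We will carry out RNA-seq of whole blood samples at baseline, day 1 and day 10", with no limit to extreme responders in that sentence. The opening of Section 1 is more general: "transcriptome and epigenetic analyses will be carried out on selected high responders and non-responders".

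**The concern.** Leave-one-out is often treated as the safe choice in small samples. With two equal classes it is not neutral. The held-out person's class is always one short in training, so any rule that leans towards the commoner class leans away from the right answer, every time.

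The sorted-cell and in-depth ATAC-seq data come in exactly this shape: 5 v 5 per vaccine, or 10 v 10 if the vaccines are pooled. The study aims to explain non-response. An accuracy that starts well below 50% under no signal does not estimate how well responder status can be told apart, and for some methods at 5 v 5 it could hide a real difference.

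**Working it through.** **1. The plan's own figure.** The plan states no classifier accuracy or classifier sample size. Its only computed design figure is the power above 90% in Section 8.2, for detecting at least 6,000 genes with 20 per cohort. Inputs from that section: 37,649 genes, SD 0.7 (log2), FDR 1%, and a two-fold difference taken as 1 log2 unit.
- Per-gene alpha = K x power x f / ((m - K)(1 - f)) = 6,000 x 0.9 x 0.01 / (31,649 x 0.99) = 0.00172.
- Normal approximation: 1 / (0.7 x sqrt(2/20)) = 4.52; 4.52 - 3.13 = 1.38 (before rounding), giving power 0.917. The noncentral t gives 0.862.
- The figure is therefore reproduced within standard variants. At the same alpha, t-test power is 0.36 for 10 v 10 and 0.07 for 5 v 5. It gives no assurance about the extreme groups or about classification.

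**2. Mechanism.** Let each class have h people. Leave-one-out trains on h - 1 of the held-out person's class and h of the other. On noise the held-out values are unrelated to the label, so expected accuracy is the chance that the rule predicts the class that is one short.
- A rule that falls back on the majority scores 0 of 2h, which is 0%.
- A rule that guesses in proportion to the training classes scores (h - 1)/(2h - 1): 4/9 = 44.4% at 5 v 5, 9/19 = 47.4% at 10 v 10, 19/39 = 48.7% at 20 v 20.
- Holding out one person per class leaves h - 1 v h - 1, and symmetry returns 50%.

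**3. Noise simulations (truth 50%).** The plan gives no feature count, selection rule or tuning, so these are assumptions. Setting A: 60 features, 160 replicates at 5 v 5 and 80 at 10 v 10. Setting B: 5,000 features, best 20 by t chosen inside each fold, 100 and 60 replicates.

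| Leave-one-out mean | A, 5 v 5 | B, 5 v 5 | B, 10 v 10 |
|---|---|---|---|
| Nearest neighbour | 39% | 32% | 46% |
| Radial-basis SVM | 0.5% | 25% | 44% |
| Linear SVM | 37% | 34% | 47% |
| Random forest | 34% | 34% | 43% |
| Boosting | 39% | 32% | 42% |

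- Setting A at 10 v 10 ranged from 14% to 49%. A third run gave 5-42% at 5 v 5 and 28-49% at 10 v 10.
- At 20 v 20, simpler stand-in classifiers with in-fold selection gave 46-48%.
- One person per class held out: 46-53% in A; 49% (5 v 5) and 49-50% (10 v 10) with stand-in classifiers and in-fold selection; 51-53% and 46-52% in the third run.
- Monte Carlo error in B: at 5 v 5 the highest mean (0.342, SD 0.24) lies (0.50 - 0.342)/(0.24/sqrt(100)) = 6.6 standard errors below 0.50. At 10 v 10 the linear SVM (0.472, SD 0.18) lies only (0.50 - 0.472)/(0.18/sqrt(60)) = 1.2 below.

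**4. With a real signal.** A small check used 60 features, 10 of them shifted by 1/0.7 = 1.43 SD (Section 8.2's two-fold difference and SD), with 30-40 replicates.
- At 10 v 10, leave-one-out gave 0.89, 0.93, 0.93 and 0.81 (nearest neighbour, radial-basis SVM, linear SVM, forest) against true values of 0.92, 0.96, 0.94 and 0.88.
- At 5 v 5, nearest neighbour and linear SVM lost 0.03-0.05, but radial-basis SVM gave 0.54 against 0.93 and forest 0.61 against 0.77.

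**5. The opposite error, if it arises.** Choosing the 20 genes once on all subjects gave noise accuracy of 0.98-1.00 at 5 v 5, 0.64-1.00 at 10 v 10, and 0.85-0.99 at 20 v 20 (stand-ins). With in-fold selection, the best of five methods still reached 70% or more on noise in 19% (5 v 5) and 42% (10 v 10) of data sets.

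**6. Precision.** In B, the SD of leave-one-out accuracy on noise was 0.19-0.24 with 10 people and 0.18-0.25 with 20. Independent predictions would give sqrt(0.25/10) = 0.158 and sqrt(0.25/20) = 0.112. A binomial interval is thus too narrow, and it is already wide: 8 of 10 correct has a 95% interval of 0.44-0.97.

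**7. Extremes v everyone.** A marker with an assumed correlation of 0.5 with response classifies 0.75 of the 5 v 5 extremes of 20, but 0.66 of all 20 split at the median.

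**The case against.** The strongest reply is that Section 8.1 never ties class prediction to the extreme groups. Whole-blood RNA-seq carries no such limit, and Table 1 lists flow cytometry at every visit, so classification could use 20 per vaccine or 40 in all. Nor need the classes be equal there: the flu pilot in Section 8.2 had eight high and six low responders, and with 8 v 6 a majority rule under leave-one-out scores 8/14 = 57%, not 0%. This stands. It limits the point to balanced classes, chiefly the sorted-cell and in-depth ATAC-seq data.

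It is also fair that the percentages move with the settings, that the loss with a real signal is modest at 10 v 10, and that no aim or power statement rests on classifier accuracy.

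Two stronger readings are tempting. A reader might infer that the plan is bound to err in both directions. It is not: inflation requires gene filtering outside the folds, or citing the best of several methods, and the plan states neither. Silence is a gap, not a faulty procedure. A reader might also see a contradiction with Section 1, which says "this study is not designed to establish baseline phenotypes predictive of vaccine responsiveness". That sentence covers baseline phenotypes only; prediction from day 1 or day 10 data would not conflict with it.

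**Conclusion.** The point holds where leave-one-out is applied to equal-sized classes. The downward bias follows from the stated validation method and needs no further assumption about conduct; only its size does. On noise it is about 25-42% instead of 50% at 5 v 5 for most methods (near 0-5% for some radial-basis kernels), about 40-49% at 10 v 10 for most methods (lower for radial-basis kernels), and usually within a few points of 50% at 20 v 20. The danger of missing a real difference is mainly at 5 v 5 and in some methods. Inflation to about 64-100% on noise is a risk that the plan leaves open, not one that it commits to. All sizes rest on assumed feature counts, selection rules and tuning. The issue concerns an exploratory analysis, but the correction is nearly free and worth making.

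**What to change.** In Section 8.1:
- Whenever the extreme groups are classified, replace leave-one-out with class-balanced hold-out: one high and one low responder together, or repeated stratified folds.
- State that gene selection and tuning are redone inside every training fold.
- Report every method run, each with a label-permutation p-value that repeats the whole pipeline. Permutation alone is not enough: it can give a valid test under leave-one-out but leaves the accuracy estimate biased.
- Limit accuracy claims from the extreme groups to extreme responders.
- Name the data set, classes and time points used for class prediction, so that a reader can see where the balanced hold-out applies.

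The cost is a few lines of text and some computing time, with no new subjects or samples. The reported accuracies may be less favourable than those from a looser procedure.
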